## 3.2.3.3 Outliers

Any outlier identified prior to database lock which is impossible / implausible will be excluded from the analysis. For other identified outliers, the impact should be assessed by performing the statistical analysis with the actual values and at least one other analysis eliminating or reducing the outlier effect.

If any outliers are identified after database lock the statistical analysis should be performed with the actual values and at least one other analysis eliminating or reducing the outlier effect.

A search of outliers by Biotrial should be performed before the database lock and actions with the sponsor should be defined. This will be done for variables used for the primary and secondary analysis: AROM against 10 prespecified muscle groups, MFS overall scores, the maximal WS barefoot, EQ-5D-5L scores (5 scores from the EQ-5D descriptive system and the EQ-5D-5L VAS score) and the answers to the

35/70

SF-12 questionnaire. A detection of abnormal values on vital signs data will also be performed.

# 3.2.4 Subject disposition

The number and percentage of subjects enrolled and included in each population will be tabulated by country and centre. A summary table (including the number of completed subjects defined as all screened subjects who completed his/her Final Visit) and a flow chart will be presented for each subject population and will be tabulated by country and centre. The reasons for subject exclusions from each of the populations will also be tabulated. In addition, the numbers of subjects who were treated will be tabulated for each population.

A listing of the inclusion and exclusion criteria will be provided and the listings of the inclusion and exclusion criteria not respected will be provided by country, centre, subject ID on all the subjects.

All the protocol deviations, defined prior to database freeze, will be listed by country, centre, subject ID on all the subjects. A frequency table of the number and percentage of subjects with at least one major protocol deviation with the number of major protocol deviations will be provided by protocol deviation class and overall on the ITT population.

The impact of major protocol deviation on the primary efficacy analysis will be investigated by comparing the results of the mITT and PP population analyses.

A listing of subjects screened with the reason for inclusion failure will be presented by country, centre and subject ID for the Enrolled population.

A listing of dates of assessments will be presented by subject ID on all the subjects.

# 3.2.5 Withdrawals

Discontinued subjects will be listed on all the subjects and a frequency table of the number and percentage of subjects who withdrew from the study and the reasons for withdrawal will be presented for the Enrolled population.

# 3.2.6 Demographic and baseline characteristics

All demographic and baseline characteristics will be listed by country, centre and subject ID for the Enrolled population.

Summary statistics or frequency tables will be provided for demographic and baseline characteristics for the ITT population. If the ITT population differs from the mITT population by more than 10%, summary statistics for demographic and baseline characteristics will also be presented for the mITT population.

# 3.2.6.1 Demographic data

The following demographic data will be summarized:

- Age: in years and in classes (<65 years /  $\geq$ 65 years)
- Sex (Male / Female)
- Race (Asian / Black or African American / White / Native Hawaiian or Other Pacific Islander / American Indian or Alaska Native / Other), except for French centers
- Ethnicity (Hispanic/Latino / Not Hispanic/Latino), except for French centers
- Height (cm)

- Body weight (kg) at baseline
- BMI (kg/m^2) at baseline
- Country (France / Czech Republic / Russia / USA)
- Selection of primary TT limb (UL / LL): this variable will be described overall and by country.
- Naïve to BoNT treatment (for UL and/or LL spasticities) (Yes / No)
- Naïve to GSC (Yes / No).
- 3.2.6.2 Other baseline characteristics

The following other baseline characteristics will be summarized:

- Disease history
  - Type of ABI (Brain trauma / Vascular (infarct or haemorrhage))
  - Duration since the date of ABI: in months and in classes ([12;18[ months / [18;24[ months / ≥24 months)
  - Time from spasticity onset: in months and in classes ([0;6[ months / [6;12[ months / [12;18[ months / [18;24[ months / ≥24 months)
  - Time between spasticity and first BoNT injection (first injection before the study for the non-naïve subjects and first injection in the study for the naïve subjects): in months and in classes ([0;6[ months / [6;12[ months / [12;18[ months / [18;24[ months / ≥24 months)
- Previous BoNT injections
  - For UL spasticity and for LL spasticity separately
    - BoNT treatment (naïve / non-naïve)
    - For non-naïve subjects to BoNT treatment: time from the first 0 BoNT injection ([0;6[ months / [6;12[ months / [12;18[ months / [18;24] months /  $\geq$ 24 months), time from the last BoNT injection ([0;6[ months / [6;12[ months / [12;18[ months / [18;24[ months / >24 months). brand name at the last injection (AbobotulinumtoxinA - DYSPORT® / OnabotulinumtoxinA -BOTOX® / IncobotulinumtoxinA - XEOMIN® or XEOMEEN® / Other) and, the time from the last BoNT injection and the total dose administered of the last injection (units) by brand
  - For non-naïve subjects previously treated with BoNT for UL and/or LL spasticity: total dose administered of the last injection (units) by brand
  - GSC
    - For non-naïve subjects to GSC only: subject satisfaction with GSC at baseline (Completely satisfied / Rather satisfied / Neither satisfied nor dissatisfied / Rather dissatisfied / Completely dissatisfied).
    - Subject's belief that the GSC will help to improve functional capacity at baseline (Very true of what I believe / Somewhat true of what I believe / No opinion/don't know / Somewhat untrue of what I believe / Very untrue of what I believe)

- Physiotherapist's belief that the GSC will help to improve functional capacity of the subject at baseline (Very true of what I believe / Somewhat true of what I believe / No opinion/don't know / Somewhat untrue of what I believe / Very untrue of what I believe)
- The AROM at baseline will be described as follows:

	Muscle group		
	Injected	Not injected	Injected or not
Overall full composite AROM: XA full (ie. sum of ten			Х
muscle groups)			
Full composite AROM			Х
- XA full UL (ie. sum of five UL muscle groups)			
- XA full LL (ie. sum of five LL muscle groups)			
Composite AROM			Х
- composite XA UL (ie. sum of X AEF ; X AWF ; X AFF )			
- composite XA LL (ie. sum of X ASol ; X AGN )			
Muscle groups	Х	Х	Х
- UL: 5 muscle groups			
- LL: 5 muscle groups			

A muscle group will be considered as injected if at least one muscle within the muscle group is injected.

- MFS overall scores, assessed locally and centrally by a reviewer blinded regarding the order of the video recording/visit number for a given subject, at baseline: these variables will be described overall and by primary TT limb.
- WST at baseline
  - Ability of the patient to walk 10 metres in 5 min or less (Yes / No)
  - Maximal WS barefoot (m/s): this variable will be described overall and by primary TT limb.
- EQ-5D-5L questionnaire at baseline
  - Answer to the 5 questions
    - Mobility (I have no problems walking / I have slight problems walking / I have moderate problems walking / I have severe problems walking / I am unable to walk)
    - Self-care (I have no problems washing or dressing myself / I have slight problems washing or dressing myself / I have moderate problems washing or dressing myself / I have severe problems washing or dressing myself / I am unable to wash or dress myself)
    - Usual activities (I have no problems doing my usual activities / I have slight problems doing my usual activities / I have moderate problems doing my usual activities / I have severe problems doing my usual activities / I am unable to do my usual activities)
    - Pain/discomfort (I have no pain or discomfort / I have slight pain or discomfort / I have moderate pain or discomfort / I have severe pain or discomfort / I have extreme pain or discomfort)
    - Anxiety/depression (I am not anxious or depressed / I am slightly anxious or depressed / I am moderately anxious or depressed / I am severely anxious or depressed / I am extremely anxious or depressed)

- Index score (for the French centers and the US centers only)
- EQ-5D-5L VAS score.
- SF-12 questionnaire at baseline: SF-12 physical score and SF-12 mental score.
- Urine pregnancy test: positive results will be listed.
- Vital signs at baseline:
  - Supine systolic blood pressure (mmHg)
  - Supine diastolic blood pressure (mmHg)
  - Supine heart rate (BEATS/min).
- Physical examination at baseline: the dates of physical examination will be listed only.

#### 3.2.7 Medical and surgical history

Medical and surgical history will be coded using MedDRA Version in force within Ipsen at the first time of first coding.

A listing will present the primary system organ class, the preferred term and the reported term for the Enrolled population. The listing of medical history will be sorted by country, centre, subject ID, primary system organ class, preferred term and reported term.

A frequency table of the number and percentage of subjects will be provided by primary system organ class and preferred term on the ITT population for:

- prior significant medical and surgical history not related to UL or LL spasticity,
- ongoing significant medical and surgical history not related to UL or LL spasticity.

#### 3.2.8 Subject compliance

#### 3.2.8.1 Subject compliance to study drug

Listings will be presented for the drug administration date, the technique used to target injection with the side injected and details of injections (muscle group injected, site of administration injected, number of injection sites, dose administered by muscle and total doses administered for each limb and for both limbs) by country, centre, subject ID, cycle, limb, muscle group and site of administration for the Enrolled population.

The study exposure (weeks) will be summarized on the safety population.

Compliance to study drug will be calculated in percentage as the total dose administered based on the expected total units to be injected (1500 U per cycle) and will be categorized as <80%, 80-120% and >120%. The overall compliance to study drug and the compliance to study drug for each cycle will be summarized in percentage and in classes, on the safety population. Compliance to study drug will also be listed by country, centre, subject ID and cycle.

A frequency table of the number and percentage of subjects with less than 750 units for the target limb and the number and the percentage of subjects injected in only one limb will be provided on the safety population.

Summary statistics of the dose administered (units) will be presented on the safety population by:

- Muscle: overall and by primary TT limb only for the muscles which are injected in at least 20% of the safety population.
- Muscle group
  - for UL limb: shoulder extensors, elbow flexors, wrist flexors, extrinsic finger flexors, pronator teres and other.
  - for LL limb: soleus, gastrocnemius, gluteus maximus, hamstrings, rectus femoris muscle, tibialis posterior, hallux flexors, adductors, gracilis and other.
- Limb (for each limb and for both limbs)
- Primary TT limb: Upper limb and Lower limb.

The technique used (ES, ultrasound and both) and the laterality will also be presented on the safety population.

Summary statistics of the time to re-injection (days) will be presented. A frequency table of the percentage of subjects re-injected will also be provided by visit during the cycle 1.

*3.2.8.2* Subject compliance to GSC

Compliance to GSC will be calculated in percentage based on the number of days when GSC therapy was not performed (as determined from the subject diary) and will be categorized as <80% and 80-100%. The overall compliance to GSC and the compliance to GSC for each cycle will be summarized in percentage and in classes, on the safety population. Compliance to GSC will also be listed by country, centre, subject ID and cycle.

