3.6 Stopping Rules and Discontinuation Criteria

In the following circumstances, subjects will be withdrawn from the study early:

- subject consent withdrawal
- subject lost to follow up
- occurrence of an AE that, in the opinion of the investigator, makes the administration of the study treatment undesirable
- investigator's and/or sponsor's decision to withdraw the subject if it is considered to be in the best interest of the subject
- occurrence of a new ABI

PROTOCOL FINAL (INCLUDING AMENDMENT #2): 24 JANUARY 2018

PAGE 33/105

- continuous failure to comply with the provisions of the study protocol, which is likely to have an adverse impact on the safety or well-being of the subject, or could jeopardise the scientific value of the study
- investigator decides that subject does not need a second AbobotulinumtoxinA administration at Week 20 in Cycle 1.

Subject withdrawal criteria and procedures are described in Section 4.3.

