# 3.2.3 Missing data and outliers

3.2.3.1 Missing data

Unless stated otherwise, no missing value will be replaced.

If a value required a retest, the last reliable non-missing value will be taken into account if measured before the administration of IMP; and the first non-missing

reliable value for post-baseline assessments. An assessment will be considered reliable if it is performed without any technical problem and if the result is within the range of plausible values. Any retest or unscheduled assessments performed will be included in the individual subject data listings.

If there is a significant number of missing values for a subject (or if there is confirmed data appearing spurious), a decision will be made following consultation with the sponsor regarding the handling of these data in summaries, during the Data Review Meeting.

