#### 3.2.16 Rules and data formats

Data will be presented using an appropriate number of decimal places (i.e. the number of decimal places used does not imply undue precision). Raw data will be presented to the number of decimal places collected, and derived data will be presented to an appropriate number of decimal places. The appropriate number of decimal places will be determined by general practice, mathematical rationale or scientific rationale (e.g. age should be presented in whole numbers).

For summary statistics of continuous data, the following will be presented n, number of missing values, arithmetic mean, standard deviation, median, first quartile and third quartile (Q1 and Q3), and the range (minimum, maximum). The 95% CIs will also be presented for the efficacy endpoints only.

For summary statistics of categorical nominal data, the following will be presented n, number of missing values and percentage of subjects for each category. The 95% CIs will also be presented for the efficacy endpoints only.

For summary statistics of categorical ordinal data, both presentations as described above will be presented.

Mean, median, Q1, Q3, standard deviation and 95% CIs for means values will be reported to one decimal place greater than the raw/derived data that they summarise. Minimum and maximum values will be reported with the same precision as the raw data.

Percentages will be reported to one decimal place and 0% will not be presented. Percentages will be calculated using a denominator of all subjects with available data in a specified population. The denominator will be specified in a footnote to the tables for clarification if necessary. Missing values will not be accounted for in denominator.

P-values will be reported to four decimal places (e.g.: p=0.0037), after rounding. P-values which are less than 0.0001 will be presented as '<0.0001'.

All text fields must be left justified and numeric or numeric with some text specification (e.g.: not done, unknown, <4.5, ...) must be decimal justified. Dates will be presented in the format [yyyy-mm-dd] and times in the format [hh:mm].

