#### (24) Time to re-injection

The time to re-injection will be calculated as (date of re-injection - date of first injection) + 1. The date of re-injection corresponds to the date when the subject was injected a second time, at the beginning of the cycle 2.

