Table 14.1.4.2.1.5.1:	Time To Re-injection - Safety Population
Table 14.1.4.2.1.5.2:	Number (%) of Subjects Re-injected by Visit during the Cycle 1 - Safety Population
Table 14.1.4.2.2:	Compliance to GSC - Safety Population
Table 14.1.4.2.3:	Compliance to Study Drug and/or GSC - Safety Population
Table 14.1.5.1:	Demographic Data - ITT Population
Table 14.1.5.2.1:	Disease History - ITT Population
Table 14.1.5.2.2:	Previous BoNT Injections - ITT Population
Table 14.1.5.2.3:	GSC - ITT Population
Table 14.1.5.2.4.1.1:	AROMs (degrees) Against Each Muscle Group at Baseline - ITT Population
Table 14.1.5.2.4.1.2:	Composite AROMs and Full Composite AROMs at Baseline - ITT Population
Table 14.1.5.2.4.2.1:	AROMs (degrees) Against Each Muscle Group at Baseline by Country - ITT Population
Table 14.1.5.2.4.2.2:	Composite AROMs and Full Composite AROMs at Baseline by Country - ITT Population
Table 14.1.5.2.4.3.1:	AROMs (degrees) Against Each Muscle Group at Baseline by Primary TT Limb - ITT Population
Table 14.1.5.2.4.3.2:	Composite AROMs and Full Composite AROMs at Baseline by Primary TT Limb - ITT Population
Table 14.1.5.2.4.4.1:	AROMs (degrees) Against Each Muscle Group at Baseline by Naïve or Non-Naïve to BoNT Treatment (for UL and LL spasticities, for UL spasticity and for LL spasticity) - ITT Population
Table 14.1.5.2.4.4.2:	Composite AROMs and Full Composite AROMs at Baseline by Naïve or Non-Naïve to BoNT Treatment (for UL and LL spasticities, for UL spasticity and for LL spasticity) - ITT Population
Table 14.1.5.2.4.5.1:	AROMs (degrees) Against Each Muscle Group at Baseline by Naïve or Non-Naïve to GSC - ITT Population
Table 14.1.5.2.4.5.2:	Composite AROMs and Full Composite AROMs at Baseline by Naïve or Non-Naïve to GSC - ITT Population

SAP Version 2.0: 05 October 2018	66/70
Table 14.1.5.2.5:	MFS (Local and Central Review) at Baseline - ITT Population
Table 14.1.5.2.6:	Maximal Walking Speed Barefoot at Baseline - ITT Population
Table 14.1.5.2.7:	EQ-5D-5L Questionnaire at Baseline - ITT Population
Table 14.1.5.2.8:	SF-12 Questionnaire at Baseline - ITT Population
Listing 14.1.5.2.9:	Positive Results for Urine Pregnancy Test - ITT Population
Table 14.1.5.2.10:	Vital Signs at Baseline - ITT Population
Table 14.1.6.1:	Significant Medical and Surgical History Not Related to UL or LL Spasticity - Prior condition - ITT Population
Table 14.1.6.2:	Significant Medical and Surgical History Not Related to UL or LL Spasticity - Ongoing condition - ITT Population

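### Time to re-injection is summarised only in re-injected subjects, so those withdrawn at Week 20 as not needing a second injection are left out and the mean interval is biased short

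*SAP*

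**What the plan says.** SAP 3.2.8.1 (Subject compliance to study drug) plans two outputs on re-injection. The first reads: "Summary statistics of the time to re-injection (days) will be presented". The second reads: "A frequency table of the percentage of subjects re-injected will also be provided by visit during the cycle 1".

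Appendix 1 (24) gives the derivation: "The time to re-injection will be calculated as (date of re-injection - date of first injection) + 1". It adds: "The date of re-injection corresponds to the date when the subject was injected a second time, at the beginning of the cycle 2". No other date is provided for a subject who has no second injection. SAP 3.2.3.1 adds: "Unless stated otherwise, no missing value will be replaced". The tables index in Appendix 3 nevertheless titles the output "Time To Re-injection - Safety Population", and the safety population (SAP 2.3) is everyone injected at least once.

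Protocol 3.6 lists among the grounds for early withdrawal: "investigator decides that subject does not need a second AbobotulinumtoxinA administration at Week 20 in Cycle 1". SAP 1.3.2.4 repeats it.

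For percentages, SAP 3.2.16 says: "Missing values will not be accounted for in denominator". The same section shows n and the number missing for continuous summaries, and allows a footnote on the denominator where needed.

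SAP section 5 lists the re-injection analyses as additions to the protocol. Time to first response was added in the same list. For that variable, SAP 3.2.1.1.2 specifies Kaplan-Meier estimation with censoring at the last study visit.

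**The concern.** Re-injection in Cycle 1 is decided at Weeks 12, 16 and 20 on whether the subject is still responding or needs another injection. A subject judged at Week 20 not to need one is withdrawn and never gets a re-injection date. What is known about that subject is that the interval is longer than the time to the Week 20 visit. This is a right-censored observation at the long end of the scale, and the planned summary treats it as missing.

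A reader who takes the reported mean as the usual time until re-injection is needed would get a figure that is too short. Interval length is of interest in this trial: Protocol 2.2 has a secondary objective on satisfaction with intervals longer than 12 weeks. The SAP already applies the suitable method to its other added time-to-event variable.

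**Working it through.** **The plan's own figures.** The documents state no expected time to re-injection and no rate of non-re-injection. The figures borrowed here are the enrolment target and the dropout allowance (Protocol 10.2). They reproduce: 1.96² × 0.6 × 0.4 / 0.08² = 144.05, rounded up to 145; 145 / 0.95 = 152.6, rounded up to 153. They serve only as a realistic N.

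**Inputs.**
- From the documents: N = 153; 5% dropout, so 8 early withdrawals and 145 others; visits at Weeks 12, 16 and 20, which on the plus-one formula of Appendix 1 (24) are days 85, 113 and 141.
- Assumed: the early withdrawals leave before Week 12. Re-injected subjects split over Weeks 12/16/20 as 70/20/10, 50/25/25 or 34/33/33. The number not needing re-injection at Week 20 is k = 0, 3, 8, 15 or 31 (0, 2, 5, 10 and 20% of 153).

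**Formula.** Let m be the mean in re-injected subjects, which is the planned statistic, and let L be the value given to each of the k subjects. The mean over all 145 exceeds m by (k / 145) × (L − m). With L = 141 this is the Kaplan-Meier mean restricted to day 141. With L = 169 each such subject is assumed to last one further four-week step.

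**Worked case** (70/20/10, k = 8; 96, 27 and 14 subjects re-injected at the three visits):
- Planned mean: (96 × 85 + 27 × 113 + 14 × 141) / 137 = 13,185 / 137 = 96.2 days.
- L = 141: (13,185 + 8 × 141) / 145 = 98.7 days, a gap of 2.5.
- L = 169: (13,185 + 8 × 169) / 145 = 100.3 days, a gap of 4.0 before rounding (100.26 − 96.24).

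**Range over the three splits.** Here m is about 96, 106 and 113 days respectively.

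| k (share of 153) | Re-injected | Gap in days, L = 141 | Gap in days, L = 169 |
|---|---|---|---|
| 0 (0%) | 145 | 0 | 0 |
| 3 (2%) | 142 | 0.6 to 0.9 | 1.2 to 1.5 |
| 8 (5%) | 137 | 1.6 to 2.5 | 3.1 to 4.0 |
| 15 (10%) | 130 | 2.9 to 4.6 | 5.8 to 7.5 |
| 31 (20%) | 114 | 6.1 to 9.6 | 12.1 to 15.6 |

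**Median.** At k = 8 the planned and Kaplan-Meier medians agree in all three splits (85, 113 and 113 days). The only differences in the grid are 99 against 113 days under 50/25/25 at k = 3, 15 and 31. There exactly half of the re-injected subjects fall at Week 12 (for example 65 of 130), so the sample median is the midpoint of 85 and 113.

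**By-visit table.** In the worked case, the share re-injected at Week 12 is 96 / 137 = 70.1% if only re-injected subjects are counted and 96 / 153 = 62.7% if all injected subjects are. The SAP does not say explicitly which denominator applies.

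**The case against.** The best reply is that this is an exposure description. It sits under compliance to study drug, its tables are numbered with exposure rather than efficacy, and the interval between two injections actually given is properly conditional on both having been given. The omission is also partly visible: the number missing is displayed, withdrawals are tabulated by reason (SAP 3.2.5), and the by-visit table carries much of the information. The median, which hardly moves, is reported as well. Kaplan-Meier brings an assumption of its own about early withdrawals.

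Most of this stands, which is why the planned summary should be kept. It does not remove the mismatch between a table titled for the safety population and statistics that can describe only part of it. Nor does it change the direction of the error in the mean if that mean is read as time until re-injection is needed.

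Three stronger readings are tempting, and the documents do not support them:
- A reader might infer that the output is meant to measure duration of effect. No text says so.
- A reader might infer that everyone not re-injected is a long responder. That group also includes withdrawals for adverse events, consent, loss to follow-up or a new brain injury, at any time in Cycle 1. Valuing them all beyond Week 20 is unjustified, and their effect on the bias is unknown.
- A reader might infer that the Week 12 share will be overstated. In a safety-population table, not re-injected is most naturally a known status rather than a missing value, so such subjects would stay in the denominator. SAP 3.2.16 leaves the other reading possible, no more.

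**Conclusion.** The point holds in a limited form. For subjects withdrawn at Week 20 because no second injection was needed, the interval is longer than the time to their own Week 20 visit, and the planned statistics leave them out. Taken as the interval until re-injection is needed, the mean is biased in one direction, short.

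At 5% of subjects the illustration gives about 2 to 4 days; at 20%, about 6 to 16 days; with no such subjects, nothing. These sizes rest on assumed visit splits and rates, and on the Week 20 decision reflecting continued benefit rather than some other reason. The median is little changed or unchanged. The output is descriptive and was added by the SAP, so the primary and secondary endpoints are unaffected. This is a cheap improvement, not a flaw in the trial's main result.

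**What to change.** 1. Keep the summary statistics, and label them in SAP 3.2.8.1 and the table title as covering re-injected subjects only.
2. Add a Kaplan-Meier (or cumulative incidence) analysis on the safety population. The event is the second injection; subjects not re-injected are censored at their last Cycle 1 visit. Put the censoring date in Appendix 1 (24), on the same plus-one scale.
3. State that the by-visit percentages use all injected subjects as denominator. Add not-re-injected rows that separate not needed at Week 20 from other withdrawal reasons.

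The cost is a few lines of SAP text, one more PROC LIFETEST call and the extra table rows. Injection dates and the primary reason for withdrawal are already collected, so no new data are needed. The drawback is that Kaplan-Meier treats early withdrawals as non-informatively censored; the rows by reason let a reader judge how much rests on that.
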